Appendix 7. Schedule Of Activities37

1. VERSION HISTORY

This is the first amendment of the Statistical Analysis Plan (SAP) for study B7451014 and is based on Protocol Amendment 5 dated 28OCT2019 and the latest Protocol Administrative Change Letter (PACL) dated 07MAY2020.

Table 1. Summary of Changes

Version/ Date	Associated Protocol Amendment	Rationale	Specific Changes
1 08 May 2018	Original 26 Feb 2018	N/A	N/A
2 22-Sep-2020	Amendment 5 28 Oct 2019	Regulatory (FDA) Input; Clarification or completion of prior version	
Added a key secondary endpoint as loss of response due to IGA of 2 or more in Table 2 and Section 3.2.1. See also, Section 6.2.
 
Added responder analyses based on HADS, DLQI/CDLQI, PtGA and PSAAD as endpoints in Sections 3.2.5 through 3.2.9. See also, Section 6.4.2.
 
Updated the definition of TEAE in Section 3.5.1.
 
Added a description of the multiple testing procedure for the primary and key secondary endpoints in Section 5.1.
 
Added disease severity at Study Baseline as a stratification factor in Sections 5.2.1 through 5.2.2.
 
Additional minor changes to improve clarity and alignment with the protocol.

2. INTRODUCTION

This SAP provides the detailed methodology for summary and statistical analyses of the data collected in study B7451014. This document may modify the plans outlined in the protocol; however, any major modifications of the primary endpoint definition or its analysis will also be reflected in a protocol amendment.

2.1. Study Objectives

Study objectives and corresponding endpoints are provided in [Table 2](#) below.

Table 2. Study Objectives and Endpoints

Primary Objective:	Primary Endpoint:

 To evaluate and compare the maintenance of effect of two doses of PF-04965842 (200 mg and 100 mg once daily (QD)) and placebo in subjects aged 12 and above with moderate to severe atopic dermatitis who respond to initial open-label run-in treatment of 200 mg PF-04965842 QD. 	
 Loss of response requiring rescue treatment will be evaluated and compared among groups during the blinded treatment period. Loss of response is denoted as flare and is defined as a loss of at least 50% of the Eczema Area and Severity Index (EASI) response at Week 12 and an Investigator’s Global Assessment (IGA) score of 2 or higher.
Secondary Objectives:	Secondary Endpoints:

 To evaluate and compare the effect of PF-04965842 on additional efficacy endpoints and patient-reported outcomes over time in subjects aged 12 years and older with moderate to severe atopic dermatitis; To assess the efficacy of open label rescue treatment consisting of 200 mg PF-04965842 in combination with topical therapy per standard of care in cases of flare (per protocol definition). 	
Key Secondary Endpoint
 
 Loss of response during the blinded treatment period based on an IGA score of 2 or higher. 
Clinical Efficacy Assessments:
 
 Response based on the IGA at all scheduled time points. Response based on EASI total score at all scheduled time points. Response based on achieving ≥ 4-point improvement in the severity of pruritus Numerical Rating Scale (NRS) from baseline at all scheduled time points. Percent change from baseline in percent Body Surface Area (BSA) at all scheduled time points. Percent change from baseline in SCORing Atopic Dermatitis (SCORAD) subjective assessments of itch and sleep loss at all scheduled time points. Response based on achieving a $\geq 50\%$ and $\geq 75\%$ improvement in SCORAD (SCORAD-50, SCORAD-75) from baseline at all scheduled time points. 
Clinical Efficacy Assessments in Subjects Requiring Rescue Treatment:
 
 Response based on the IGA at the end of rescue therapy. Response based on the EASI total score at the end of rescue therapy.

	
 • Response based on achieving ≥ 4-point improvement in the severity of pruritus Numerical Rating Scale (NRS) at the end of rescue therapy relative to the start of rescue therapy baseline value. • Percent change in percent Body Surface Area (BSA) at the end of rescue therapy relative to the start of rescue therapy baseline value. • Percent change in SCORAD subjective assessments of itch and sleep loss at the end of rescue therapy relative to the start of rescue therapy baseline value. • Response based on achieving a $\geq 50\%$ and $\geq 75\%$ improvement in SCORAD (SCORAD-50, SCORAD-75) at the end of rescue therapy relative to the start of rescue therapy baseline value. 
Patient-Reported Outcomes in All Subjects:
 
 1. Response based on achieving Patient Global Assessment (PtGA) score of clear (0) or almost clear (1); and a reduction from baseline of ≥ 2 points at all scheduled time points (among subjects with a score ≥ 2 at baseline). 2. Change from baseline in Dermatology Life Quality Index (DLQI) or Children’s DLQI (CDLQI) at all scheduled time points. 3. Change from baseline in Hospital Anxiety Depression Scale (HADS) at all scheduled time points. 4. Change from baseline in Patient Oriented Eczema Measure (POEM) at all scheduled time points. 5. Change from baseline in the Pruritus and Symptoms Assessment in Atopic Dermatitis (PSAAD) at all scheduled time points.
Safety Objective:	Safety Endpoints:

 • To assess the safety and tolerability of PF-04965842 during open label and double blind treatment in subjects aged 12 and over with moderate to severe AD. 	
 • Incidence of treatment emergent adverse events. • Incidence of Serious Adverse Events (SAE)s and Adverse Events (AE)s leading to discontinuation. • The incidence of clinical abnormalities and change from baseline in clinical laboratory values, electrocardiogram (ECG) measurements, and vital signs.
Pharmacokinetic Objective:	Pharmacokinetic Endpoint:

 • To evaluate the PK of PF-04965842 in subjects aged 12 years and older with moderate to severe atopic dermatitis following 	
 1. Population PK characterization in subjects aged 12 years old and above with moderate to severe atopic dermatitis.

12 weeks of maintenance treatment.	
CCI	
	

AD = Atopic dermatitis; AE = Adverse Event; BSA = Body Surface Area; CDLQI = Children’s Dermatology Life Quality Index; DLQI = Dermatology Life Quality Index; EASI = Eczema Area and Severity Index; ECG = Electrocardiogram; EQ-5D-5L = EuroQol; Quality of Life measure; 5-Dimension 5-Level Scale; EQ-5D-Y = EuroQol Quality of Life 5-Dimension Youth Scale; FACIT-F = Functional Assessment of Chronic Illness Therapy Fatigue Scale; Peds-FACIT-F = Pediatric FACIT-F; HADS = Hospital Anxiety and Depression Scale; IGA = Investigator’s Global Assessment; NRS = pruritus numerical rating scale; PK = pharmacokinetics; SCORAD = Scoring Atopic Dermatitis; POEM = Patient-Oriented Eczema Measure; PtGA = Patient Global Assessment; PSAAD = Pruritus and Symptoms Assessment for Atopic Dermatitis; QD = Once Daily; SF-36 = Short Form-36; SAE = Serious Adverse Event.
	

[figure not shown]

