### **9.2.4. Analysis of Secondary Endpoints**

In general, binary endpoints (such as EASI-50, EASI-90 or the proportion of subjects achieving  $\geq 4$  point improvement in severity of pruritus NRS measure) will be analyzed using the (Cochran-Mantel-Haenszel) test adjusted by randomization strata (age groups) and baseline disease severity. The difference between treatment groups in the proportion of subjects achieving a response along with its 95% confidence interval (using the normal approximation for the difference in binomial proportions) will be reported. If a subject withdraws from the study, then this subject will be counted as a non-responder for endpoints

after withdrawal. In addition, a subject in the FAS-RA subset who receives rescue treatment due to protocol-defined flare will be considered a non-responder.

For continuous endpoints, such as percent change from baseline in the EASI total score and BSA or change from baseline in SCORAD, PSAAD, DLQI/CDLQI, POEM, HADS, and change from baseline in the pruritus severity using the NRS measure, a mixed-effect model with repeated measures (MMRM) will be used. This model will include the factors (fixed effects) for treatment group, randomization strata (age groups), and baseline disease severity, visit, treatment-by-visit interaction, and relevant baseline value. Within the framework of MMRM, differences between groups will be tested using estimates from the MMRM model.

For all binary endpoints, missing data will be handled by considering subjects who withdraw or randomized subjects receiving rescue treatment as non-responders. No imputations will be made for continuous data and missing data will be considered to be MAR.

In general all secondary endpoints will be analysed for the FAS-RA subset. For the subjects requiring rescue therapy (FAS-RE subset), the response achieved at the end of the rescue period will be assessed in relation to the start of the rescue period. In addition to these two analysis sets, secondary endpoints will also be summarized for all subjects participating in the open-label run-in period (FAS-OL subset).

Hypotheses for all relevant secondary endpoints will be tested at the nominal 5% level of significance, without adjustments for multiple comparisons.

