6.3. Secondary Endpoints (Efficacy)

6.3.1. Response Based on (IGA, EASI-50, EASI-75, EASI-90, EASI-100, NRS4 for Severity of Pruritus, SCORAD50 and SCORAD75, IGA + EASI-75)

	All Randomized Subjects	Randomized Subjects Requiring Rescue Treatment	Pre- Randomization Subjects
Summary	Proportion of subjects achieving a response at Weeks 12, 16, 28, 40 and 52	Proportion of subjects achieving a response at Rescue Weeks 2, 4, 8 and 12	Proportion of subjects achieving a response at Weeks 2, 4, 8 and 12
Population	FAS-RA	FAS-RE	FAS-OL
Baseline	Study (see Section 3.4)	Rescue (see Section 3.4)	Study (see Section 3.4)
Statistical Method	CMH and normal approximation as in Section 5.2.1 .	Normal approximation as in Section 5.2.1 .	Normal approximation as in Section 5.2.1 .
Missing Data	Missing values after dropout are defined as “non-response” (see Section 5.3.1)	Missing values after dropout are defined as “non-response” (see Section 5.3.1)	Missing values after dropout are defined as “non-response” (see Section 5.3.1)

6.3.2. Change from Baseline in (Total EASI Score, SCORAD (VAS) Pruritus and Sleep Sub-Scales, PP-NRS for Severity and Percent BSA)

	All Randomized Subjects	Randomized Subjects Requiring Rescue Treatment
Summary	Change from baseline at Weeks 12, 16, 28, 40 and 52	Percent change/Change from baseline at Rescue Weeks 2, 4, 8 and 12
Population	FAS-RA	FAS-RE
Baseline	Study (for Week 12); Randomization (for visits after Week 12) (see Section 3.4)	Rescue (see Section 3.4)
Statistical Method	MMRM as in Section 5.2.2	MMRM as in Section 5.2.2
Missing Data	Use observed data (see Section 5.3.2)	

Change from Study Baseline at Week 12 and its 95% CI will be estimated for each randomized treatment group using an MMRM analysis using data from Weeks 2, 4, 8 and 12. For PP-NRS, data will be included from Days 2 – 15, Weeks 4, 8 and 12.

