9. APPENDICES

Appendix 1. Summary of Clinical Efficacy Analyses

Clinical Efficacy Endpoints	Analysis Set	Baseline	Analysis Method	Missing Data Imputation	Primary Analysis for Primary Endpoint
Loss of Response	FAS-RA	Randomization Date	Time to Event	CAR	Yes
Loss of Response	PPAS	Randomization Date	Time to Event	CAR	No
Loss of Response	FAS-RA	Randomization Date	Time to Event	CNAR	No
Loss of Response based on the IGA score	FAS-RA	Randomization Date	Time to Event	CAR	
Loss of Response based on the IGA score	PPAS	Randomization Date	Time to Event	CAR	
Weeks 2, 4, 8 and 12 IGA Response	FAS-OL	Study	Normal approx.	NR	
Weeks 12, 16, 28, 40 and 52 IGA Response	FAS-RA	Study	CMH and Normal approx.	NR	
Rescue Weeks 2, 4, 8 and 12 IGA Response	FAS-RE	Study	Normal approx.	NR	
Weeks 12, 16, 28, 40 and 52 EASI-50 Response	FAS-RA	Study	CMH and Normal approx.	NR	
Weeks 2, 4, 8 and 12 EASI-75 Response	FAS-OL	Study	Normal approx.	NR	
Weeks 12, 16, 28, 40 and 52 EASI-75 Response	FAS-RA	Study	CMH and Normal approx.	NR	
Rescue Weeks 2, 4, 8 and 12 EASI-75 Response	FAS-RE	Study	Normal approx.	NR	
Weeks 12, 16, 28, 40 and 52 EASI-90 Response	FAS-RA	Study	CMH and Normal approx.	NR	
Weeks 2, 4, 8 and 12 NRS4 Severity Response	FAS-OL	Study	Normal approx.	NR	
Weeks 12, 16, 28, 40 and 52 NRS4 Severity Response	FAS-RA	Study	CMH and Normal approx.	NR	
Rescue Weeks 2, 4, 8 and 12 NRS4 Severity Response	FAS-RE	Study	Normal approx.	NR	
Weeks 12, 16, 28, 40 and 52 SCORAD50 Response	FAS-RA	Study	CMH and Normal approx.	NR	
Rescue Weeks 2, 4, 8 and 12 SCORAD50 Response	FAS-RE	Study	Normal approx.	NR	
Weeks 12, 16, 28, 40 and 52 SCORAD75 Response	FAS-RA	Study	CMH and Normal approx.	NR	
Rescue Weeks 2, 4, 8 and 12 SCORAD75 Response	FAS-RE	Study	Normal approx.	NR	
Weeks 12, 16, 28, 40 and 52 CFBL in Total EASI Score	FAS-RA	Randomization	MMRM	OD	
Rescue Weeks 2, 4, 8 and 12 PCFBL in Total EASI Score	FAS-RE	Rescue	MMRM	OD	
Weeks 12, 16, 28, 40 and 52 CFBL in Total SCORAD Score	FAS-RA	Randomization	MMRM	OD	
Rescue Weeks 2, 4, 8 and 12 PCFBL in Total SCORAD Score	FAS-RE	Rescue	MMRM	OD	
Weeks 12, 16, 28, 40 and 52 CFBL in NRS Score for Severity	FAS-RA	Randomization	MMRM	OD	
Rescue Weeks 2, 4, 8 and 12 CFBL in NRS Score for Severity	FAS-RE	Rescue	MMRM	OD	
Weeks 12, 16, 28, 40 and 52 CFBL in Percent BSA	FAS-RA	Randomization	MMRM	OD	
Rescue Weeks 2, 4, 8 and 12 PCFBL in Percent BSA	FAS-RE	Rescue	MMRM	OD	

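### The SAP compares randomized arms on absolute change in %BSA and SCORAD itch and sleep loss, but the declared secondary endpoints are percent change

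*SAP*

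**What the plan says.** **Endpoint definitions.** SAP Table 2 (Section 2.1) lists "Percent change from baseline in percent Body Surface Area (BSA) at all scheduled time points" and "Percent change from baseline in SCORing Atopic Dermatitis (SCORAD) subjective assessments of itch and sleep loss at all scheduled time points". Protocol Table 1 defines both in the same way. In its analysis text, protocol 9.2.4 names "percent change from baseline in the EASI total score and BSA or change from baseline in SCORAD" among the continuous endpoints for the mixed model.

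**Analysis in the body of the SAP.** Section 6.3.2 is headed "Change from Baseline in (Total EASI Score, SCORAD (VAS) Pruritus and Sleep Sub-Scales, PP-NRS for Severity and Percent BSA". Its FAS-RA column gives the summary measure as "Change from baseline at Weeks 12, 16, 28, 40 and 52" and the baseline as "Study (for Week 12); Randomization (for visits after Week 12". Only the FAS-RE column mentions the other scale: "Percent change/Change from baseline at Rescue Weeks 2, 4, 8 and 12".

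**Analysis in the summary table.** For %BSA, SAP Appendix 1 lists CFBL in FAS-RA and PCFBL in FAS-RE. Its footnote defines these as two separate measures. The FAS-RA row for SCORAD as a continuous variable is "CFBL in Total SCORAD Score". Neither set has a row for itch or sleep. The FAS-RA rows for continuous variables give Randomization as the baseline for every visit from Week 12 to Week 52.

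**Where arms are compared.** SAP 5.2 and the opening of SAP Section 6 restrict treatment comparisons to FAS-RA.

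**The concern.** Percent change is declared, but the plan produces it only in the rescue set, where no arms are compared. The randomized comparison would appear on a scale that the endpoint list does not name.

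There is also a practical risk. Someone programming from Appendix 1 would produce change in total SCORAD, which Table 2 does not list, and omit the itch and sleep analyses that 6.3.2 calls for. Someone programming from 6.3.2 would do the reverse. If this is settled after unblinding, the choice of scale and baseline will look as though it was made with the results in view.

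**Working it through.** The plan gives no figure to reproduce here, so the check sets the passages side by side.

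| Item | Protocol Table 1 and SAP Table 2 | Protocol 9.2.4 | SAP 6.3.2, FAS-RA | SAP Appendix 1, FAS-RA |
|---|---|---|---|---|
| %BSA | percent change | percent change | absolute change | absolute change |
| SCORAD itch, sleep | percent change | SCORAD unqualified: plain change | absolute change | no row |
| SCORAD total, continuous | not declared | SCORAD unqualified: plain change | not named | absolute change |
| Baseline for Week 12 | not specified | not specified | Study | Randomization |
| Baseline after Week 12 | not specified | not specified | Randomization | Randomization |

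**Step 1: is this shorthand?** No. Appendix 1 defines CFBL and PCFBL separately and uses both for %BSA, one in each set. Section 6.3.2 makes the same split between its columns.

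**Step 2: is it a documented change?** The SAP version history names the added key secondary endpoint, responder analyses, the TEAE definition, multiple testing and the stratification factor. It then mentions minor changes for clarity and alignment with the protocol. A move from percent to absolute change is not listed, and SAP Table 2 still states percent change.

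**Step 3: are the two measures interchangeable?** No. Take hypothetical %BSA values, which are assumptions and not trial data.

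- Arm A: 1 to 4 and 10 to 12. Mean change (3 + 2)/2 = +2.5 points; mean percent change (300% + 20%)/2 = +160%.
- Arm B: 10 to 14 twice. Mean change (4 + 4)/2 = +4.0 points; mean percent change (40% + 40%)/2 = +40%.

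Arm B worsens more in points and arm A more in percent. A starting value of 1% could occur only at Randomization Baseline, because entry requires at least 10%. The example shows that the ordering can reverse, not how often it would. The scales also weight subjects differently from Study Baseline: a fall of 5 points is 5/10 = 50% for a subject entering at 10% and 5/50 = 10% for one entering at 50%.

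**Step 4: is percent change workable?** It depends on the denominator.

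- %BSA from Study Baseline: inclusion criterion 3 requires at least 10% at the baseline visit, so the denominator is well away from zero.
- SCORAD itch and sleep from Study Baseline: each runs from 0 to 10 and has no entry minimum. The pruritus NRS criterion is a different instrument. A zero is possible, and percent change is then undefined.
- Any of the three from Randomization Baseline: responders may have IGA 0, so zeros are possible here too.

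**Step 5: the Week 12 baseline.** SAP 3.4 takes Randomization Baseline from the last observation between the last run-in dose and the first randomized dose. The protocol gives that last run-in dose at the Week 12 visit. Where one observation serves as both the Week 12 value and the Randomization Baseline, the Week 12 change in Appendix 1 is zero by construction. Section 6.3.2 avoids this by using Study Baseline for Week 12.

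**The case against.** Several stronger readings are tempting, and the documents do not support them.

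- A reader might infer that the itch and sleep analyses have been replaced by total SCORAD. They have not. Section 6.3.2 names both sub-scales, with the mixed model, in FAS-RA and FAS-RE. Appendix 1 is only a summary and lacks other rows too: EASI-100 and the combined IGA and EASI-75 response are in 6.3.1 but not there.
- A reader might infer that these variables get no randomized comparison. Sections 6.3.2 and 5.2.2 do give pairwise comparisons in FAS-RA. What is missing is the declared scale.
- A reader might infer that a required protocol amendment was skipped. SAP Section 2 lets the SAP modify the protocol and promises an amendment only for major changes to the primary endpoint or its analysis. Protocol Section 9 has a similar rule.
- A reader might infer that %BSA, itch and sleep are close to zero at randomization. No document gives those values. The responder criteria constrain IGA and EASI, and the SAP's own worked example has an EASI of 10 at Week 12.

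Two further points carry weight. For SCORAD, absolute change agrees with protocol 9.2.4, so that half of the point is weaker than the %BSA half. Also, Table 2 says only that change is from baseline, and SAP 3.4 allows three baselines, so Study Baseline as the denominator is a reasoned choice rather than something the plan dictates.

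None of this reconciles SAP Table 2 with 6.3.2 and Appendix 1. The permission to modify the protocol cannot settle a conflict within the SAP. The risk of zero denominators argues for choosing the baseline with care, not for leaving the declared measure out.

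**Conclusion.** The point holds as an inconsistency within the SAP, and it is wrong as written chiefly for %BSA. There, both endpoint lists and protocol 9.2.4 say percent change, while 6.3.2 and Appendix 1 say absolute change for the randomized set. For SCORAD itch and sleep, Table 2 conflicts with 6.3.2 in the same way, but the protocol is divided. Appendix 1 needs aligning with 6.3.2 on the sub-scales and the Week 12 baseline.

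Two listed endpoints, covering three variables, have no FAS-RA analysis on their declared scale. They lie outside the gatekeeping sequence and are tested at nominal 5%, so the error rate, power and primary result are unaffected. The conclusion rests on the text alone. How far results on the two scales would differ cannot be known from the documents.

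**What to change.** Before unblinding, amend SAP 6.3.2 and Appendix 1 as follows:

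- For FAS-RA, add percent change from Study Baseline in %BSA and in SCORAD itch and sleep loss.
- State that subjects with a zero baseline on a sub-scale are excluded from its percent change, and report how many per arm.
- Keep absolute change from Randomization Baseline as supportive.
- Add itch and sleep rows to Appendix 1 for FAS-RA and FAS-RE. Keep the total SCORAD row, because protocol 9.2.4 refers to SCORAD without qualification, and mark it as additional to Table 2.
- Use the same baseline for Week 12 in 6.3.2 and Appendix 1.
- Record the change in the version history.

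The data are already collected, so the cost is some SAP wording, a few extra tables, and the loss of zero-baseline subjects from the sub-scale percent changes.

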2.2. Study Design

This is a randomized, responder-enriched, double-blind, placebo-controlled, Phase 3 withdrawal trial to evaluate the efficacy and safety of PF-04965842 monotherapy in subjects aged 12 years and older with chronic moderate to severe AD as defined per the inclusion criteria and a body weight ≥ 40 kg.

The trial consists of an open-label run-in period to determine responder status to an initial induction treatment with 200 mg PF-04965842 QD, a randomized, placebo-controlled, double-blinded PF-04965842 maintenance treatment period, and a 4-week untreated follow-up safety period. A study design schematic is presented in [Figure 1](#).

Figure 1. Study Design Schematic

Note: Flare is defined as a loss of response associated with a decrease of at least 50% of the EASI response compared to randomization and an IGA score of ≥ 2 .

Responder criteria are defined as a) achieving an IGA of clear (0) or almost clear (1) (on a 5-point scale), b) a reduction from IGA baseline of ≥ 2 points, and c) reaching an EASI-75 response (at least 75% improvement). Subjects not meeting criteria are declared as non-responders and are not eligible for randomization in this study. They may choose to enroll into the PF-04965842 Long Term Extension (LTE) study B7451015 providing they remain eligible; otherwise, they are permanently discontinued from treatment and enter the 4-week untreated follow-up period in this study.

Responders at the end of the 12-week open-label run-in period enter the 40 week, double-blind, maintenance treatment period in which they are randomized 1:1:1 into either PF-04965842 200 mg QD, PF-04965842 100 mg QD or placebo. Randomization is stratified by age category, ie, <18 years and ≥ 18 years.

Following completion of the 40-weeks of blinded treatment, all subjects are to be assessed for eligibility to enter study B7451015. If a subject discontinues prematurely or is not eligible/willing to participate in B7451015, then the subject enters the 4-week untreated follow-up period.

During the blinded treatment period, subjects meeting the protocol definition of flare enter an open-label rescue period during which they receive another 12-week course of PF-04965842 200 mg QD with topical therapy per local standard of care (SOC). In this study, flare

requiring rescue treatment will be defined as a loss of at least 50% of the EASI response at Week 12 and an IGA score of 2 or higher.

After completing the 12-week rescue period, eligible subjects may enter study B7451015. Subjects discontinuing early from treatment, or who are otherwise ineligible for the LTE study will undergo a 4 week follow-up period in B7451014.

The total study duration if a subject does not flare is 52 weeks (12 weeks open-label treatment + 40 weeks blinded treatment). The maximum study duration is up to 64 weeks. This would only be achieved if a subject flared on the last day of the maintenance treatment period (52 weeks +12 weeks rescue). If subjects do not intend to enroll in the LTE study, the above durations are extended by +4 weeks of an untreated follow-up period.

A full schedule of activities for the study is provided in [Appendix 7](#).

Sample Size Determination

A total of 600 subjects with 200 receiving PF-04965842 200 mg QD, 200 receiving PF-04965842 100 mg QD, and 200 receiving placebo (1:1:1 randomization) will provide 94% power to detect a ratio of median time to flare of at least 1.5 times between either dose of PF-04965842 (200 mg or 100 mg) and placebo. The Type I error rate is set at 5% (2-sided). Assuming that about 44% of subjects would meet the protocol-defined criteria to be a responder at Week 12, (based on prior data), approximately 1370 subjects would need to enter the open label run-in period of the study to ensure that 600 subjects are available for randomization.

